7.2.2.2 Data Handling of eDiary records

- (1) If there is inconsistency between start date and end date of a record for sunlight exposure, the following handling rule will be adapted.
 - If recorded end date is later than start date, end datetime will be changed to 23:59 on the same day of the start date.
 - If recorded start date is later than end date/time, the record will not be used for analysis.
- (2) If there is inconsistency between start date/time and end date/time of a record for prodromal symptom or phototoxic reaction, the following handling rule will be adapted.
 - If recorded end date/time is later than start date/time, keep as it is.
 - If recorded start date/time is later than end date/time, the record will not be used for calculation each time duration but used for counting the number of each event or summarizing the intensity of each event.
- (3) How to handle missing data for prodromal symptom and phototoxic reaction start/end time:

For prodromal symptom and phototoxic reaction start/end date missing, complete with the following handling rule after sorting by subject, day, and the linked sunlight exposure start time.

For the end time of prodromal symptom and phototoxic reaction missing, the earliest datetime of following three datetime after the linked sunlight exposure end time will be used as the end datetime.

1. Start datetime of next sunlight exposure record
2. Start/end datetime of next prodrome symptom or phototoxic reaction record
3. 23:59 of the day of linked sunlight exposure record

For the start time of prodromal symptom and phototoxic reaction missing, the latest datetime of following three datetime will be used as the start datetime.

1. End datetime of prior sunlight exposure record.
2. Start/end datetime of prior prodrome symptom or phototoxic reaction record
3. 0:00 of the day of linked sunlight exposure record

For the start/end time of prodromal symptom and phototoxic reaction missing without a linked sunlight exposure record, complement with the same rules as above after sorting by subject, the entry date time.

- (4) How to handle overlapping of eDiary start/end time:

For sunlight exposure records, complete with the following handling rule after sorting by subject, day, and the linked sunlight exposure start time to remove the overlapping among records by subjects and day.

1. Compare the record's end time with next record's start time.

2. Combine them into one record and use the latest end time if end time is after the next start time.

7.2.2.3 Derivation Rule for Efficacy Endpoints from eDiary records

7.2.2.3.1. The average daily sunlight exposure time (minutes) to first prodromal symptom associated with sunlight exposure

The following is the procedure to calculate the average daily time to first prodromal symptom associated with exposure to sunlight after removing overlapping among records. The analysis windows are defined in the Table 2 Analysis Visit Window for diary data.

1. If the sunlight exposure time is beyond the interval (from 1 hour post sunrise to 1 hour pre-sunset), then this time is excluded by comparing the sunrise/sunset time.
2. A diary day is qualified if the subject had non-zero duration of sunlight exposure in the day.
3. The time to first prodromal symptom associated with exposure to sunlight in a day is calculated. It is the sum of the sunlight exposure time before occurring the first prodromal symptom or phototoxic reaction associated with sunlight exposure (which means to occur after 1st sunlight exposure in a day) in the day. If a subject had sunlight exposure but no prodromal symptom in a day, the sum of the sunlight exposure time for the day is used as the sunlight exposure time to the first prodromal symptom.
4. The average daily sunlight exposure time to the first prodromal symptom at a time point (Baseline, Week 2, 4, 6, 8, 10, 12, 14, 16, ..., 24, 26, 39, 52 and Follow-up for each period) is the average of the sunlight exposure time to the first prodromal symptom of qualified days in the corresponding 14 day window. At least 1 day diary data is required for each 14 day window to be qualified for this calculation.
5. The minute is used as the unit for calculation of the duration. The duration will not be rounded. However, in data presentation for listings, the duration will be rounded to integer. For tables, the duration will be rounded to integer for minimum and maximum and to one decimal place for mean, SD, median, and confidence intervals.

7.2.2.3.2. The average daily mean intensity on an 11-point Likert scale of the subject's prodromal symptoms

The following is the procedure to calculate the average daily mean intensity on an 11-point Likert scale of the subject's sunlight-induced (equal to associated with sunlight exposure)

prodromal symptoms. The analysis windows are defined in the Table 2 Analysis Visit Window for diary data.

1. A day without any prodromal symptoms is not qualified.
2. The mean intensity on an 11-point Likert scale of the subject's prodromal symptoms in a day is calculated. It is the average of all the intensity on an 11-point Likert scale of the subject's sunlight-induced prodromal symptoms in the day. The average daily mean intensity on an 11-point Likert scale of the subject's prodromal symptoms at a time point (Baseline, Week 2, 4, 6, 8, 10, 12, 14, 16, ..., 24, 26, 39, 52 and Follow-up for each period) is the average of the daily mean intensity of qualified days in the corresponding 14 day window. At least 1 day diary data is required for each 14 day window to be qualified for this calculation.

The following endpoint is derived when applying the similar rule as above.

- The average daily mean intensity of the subject's phototoxic reactions (associated with sun exposure) on an 11-point Likert scale

7.2.2.3.3. The average daily duration of sunlight exposure regardless of time of day without prodromal symptoms

The following is the procedure to calculate the average daily mean duration of sunlight exposure regardless of time of day without prodromal symptoms. The analysis windows are defined in the Table 2

1. Step 1 in section 7.2.2.3.1 will not be applied.
2. A diary day is qualified if the subject had non-zero duration of sunlight exposure in the day.
3. The duration of sunlight exposure without prodromal symptoms in a day is calculated. It is the sum of the duration of sunlight exposure time deducting the prodromal symptom or phototoxic reaction presenting time covered in each period.
4. Step 4 to 5 in section 7.2.2.3.1 will be applied.

7.2.2.3.4. Total number of sunlight-induced pain events defined as prodromal symptoms (burning, tingling, itching, or stinging) with pain rating of 1-10 on the Likert scale

The following is the procedure to calculate this endpoint.

1. If a subject had sunlight exposure with any prodromal symptom with pain rating of 1-10 on the Likert scale in a day, the sum of the number of events for the day is used as the number of sunlight-induced pain events in the day.
2. The sum of the number of the above events in each day during the 26-week DBT or DBE period (from Baseline date to Week 26 or from Week 26 to Week 52) is calculated as this endpoint.

The following endpoint is derived when applying the similar rule as above.

- Total number of sunlight-induced non-prodrome, phototoxic reactions
- Total number of sunlight-induced pain events defined as phototoxic events

7.2.2.3.5. Total time (hours) in duration of sunlight exposure between 1 hour post sunrise and 1 hour pre-sunset without prodromal symptoms.

The following is the procedure to calculate this endpoint.

1. Step 1 in section 7.2.2.3.1 will be applied.
2. The duration of sunlight exposure without prodromal symptoms and without phototoxic reactions in a day is calculated.
3. The sum of the above duration in each day during the 26-week DBT or DBE period (from Baseline date to Week 26 or from Week 26 to Week 52) is calculated as this endpoint.

The following endpoint is derived when applying the similar rule as above. Total time (hours) in duration of sunlight exposure between 1 hour post sunrise and 1 hour pre-sunset without prodromal symptom with the severity of greater than 0 on 11-point Likert scale and without phototoxic reactions (pain-free time hours)

The following endpoint is derived as pain-free days when applying the similar rule as above.

- Total number of days subject is exposed to sunlight for any duration between 1 hour post-sunrise and 1 hour pre-sunset without prodromal symptoms
- Total number of days subject is exposed to sunlight for any duration between 1 hour post-sunrise and 1 hour pre-sunset without prodromal symptom with the severity of greater than 0 on 11-point Likert scale and without phototoxic reactions (pain-free days)

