6 STUDY OBJECTIVES AND ENDPOINTS

6.1 Study Objectives

6.1.1 Primary Objective

- To investigate the efficacy of MT-7117 on time to onset and severity of first prodromal symptoms (burning, tingling, itching, or stinging) associated with sunlight exposure in adults and adolescents with EPP or XLP.

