10.7 Efficacy Assessments

10.7.1 Primary Efficacy Endpoint

10.7.1.1 Sunlight Exposure Diary – Outdoor Exposure and Prodromal Symptoms

Subjects will complete the sunlight exposure diary on a daily basis from Screening to the follow-up visit. The sunlight exposure diary is a smartphone device and examples of the questions (extract) are presented in Section 18.4 (Appendix 4).

Subjects will record their sunlight exposure time in the sunlight exposure diary. For each sunlight exposure, they will record the presence, duration (onset time of the first symptom and recovery time), and severity of the prodromal symptoms (see below). The severity of prodromal symptoms will be measured using an 11-point Likert scale ranging from 0 to 10, with 0 indicating no pain or discomfort and 10 indicating greatest severity of pain.

Prodromal symptom is the terminology used for the warning signals that have been described by EPP and XLP patients through patient roundtable discussions and literature as their signal to get out of the sun. Subjects will be instructed to recognize the following photo-induced symptoms as prodromal:

- Burning/hotness/heating up
- Tingling
- Itching/scratchy
- Stinging
- Others

Subject responses in the sunlight exposure diary will be used to investigate the primary efficacy endpoint. The data from the diary will also be used for the secondary and other efficacy assessments.

Further details will be provided in a separate study reference manual, and statistical assessment methods for this study endpoint are described in Section 14.3.2.1.

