7.3 Analysis Visit Definitions

(1) eDiary data excluding in-clinic sunlight exposure test

The subjects will, in their diaries, record the sunlight exposure periods (start/end time), prodromal symptom periods, and pain periods. The subjects' sunlight exposure start and end times will be compared with their state capital cities sunrise and sunset times.

The analysis windows are defined in the table below. The nominal day for each week relative to the first dose day will be used. Day 1 is the first dose day.

Table 2 Analysis Visit Window for diary data

Analysis Visit	Nominal day	Analysis Visit Window for DBT analysis
Baseline*	Day 1	Day -14 to -1
Week 2	Day 15	Day 1 to 14
Week 4	Day 29	Day 15 to 28
Week 6	Day 43	Day 29 to 42
Week 8	Day 57	Day 43 to 56
Week 10	Day 71	Day 57 to 70
Week 12	Day 85	Day 71 to 84
Week 14	Day 99	Day 85 to 98
Week 16	Day 113	Day 99 to 112
Week 18	Day 127	Day 113 to 126
Week 20	Day 141	Day 127 to 140
Week 22	Day 155	Day 141 to 154
Week 24	Day 169	Day 155 to 168
Week 26 (DBT EOT)	Day 183	Day 169 to 182
Week 26 (DBE Baseline)	Day 183	Day 169 to 182
Week 28	Day 197	Day 183 to 196
Week 32	Day 225	Day 211 to 224
Week 39	Day 274	Day 260 to 273
Week 52 (DBE EOT)	Day 365	Day 351 to 364
EOT for DBT	Day 182 or discontinued during DBT	14 days before EOT for DBT
EOT for DBE	Day 365 or discontinued during DBE	14 days before EOT for DBE
Follow-up until Week 32 (DBT EOS)	6 weeks after EOT for DBT	the latest 1 to 14 days before Follow-up date not overlapping with treatment duration in DBT period
Follow-up until Week 58 (DBE EOS)	6 weeks after EOT for DBE	the latest 1 to 14 days before Follow-up date not overlapping with treatment duration in DBE period

During 26 weeks (DBT)	1 to 182	Day 1 to EOT for DBT period
During 26 weeks (DBE)	183 to 364	DBE Baseline to EOT for DBE period

* If subjects have at least 1 day between Day -1 and Day -14, the baseline value will be calculated from the data between Day -1 and Day -14. If subjects have no data of sunlight exposure between Day -1 and Day -14, then the Analysis Visit window will be expanded to Day -28 and the baseline value will be calculated from the data between Day -1 and Day -28.

(2) Non-diary data including in-clinic sunlight exposure test

Table 3 Analysis Visit Window for non-diary efficacy data

Analysis Visit	Nominal day	Analysis Visit Window
Baseline	First dose day	NA
Week 4	Day 29	Day 16 to 64
Week 12	Day 85	Day 72 to 119
Week 26 (DBT EOT)	Day 183	Day 134 to 202

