8.2.3 Exploratory Efficacy Endpoints

The following exploratory efficacy endpoints will be analysed using the similar model as specified for the primary analysis (MMRM) replacing the baseline average daily sunlight exposure time to first prodromal symptom as covariate with the corresponding covariates at baseline visit in the below bullets.

- Change from baseline in the average daily mean intensity on an 11-point Likert scale of the subject's prodromal symptoms over time during 26-week double-blind treatment period.
- Change from baseline in average daily duration (minutes) of prodromal symptoms during 26-week double-blind treatment period.

- Change from baseline in the average daily mean intensity of the subject's phototoxic reactions (associated with sun exposure) during 26-week double-blind treatment period on an 11-point Likert scale.
- Change from baseline in average daily duration (minutes) of phototoxic reactions (associated with sun exposure) during 26-week double-blind treatment period.
- Change from baseline for all total score and total score in each domain of, anxiety, depression, fatigue, sleep disturbance, ability to participate in social roles and activities, and pain interference in the PROMIS-57
- Change from baseline in PGIS at each visit.

The following endpoints will be analysed using the same negative binomial model with log link as specified for the secondary efficacy endpoint.

- Total number of sunlight-induced pain events defined as phototoxic events during 26-week double-blind treatment.
- Total number of sunlight-induced non-prodrome, phototoxic reactions during 26-week double-blind treatment.

The following endpoint will be analysed using the same logistic regression model as specified for the secondary efficacy endpoint.

- The percentage of subjects who are responders at Week 26 based on PGIC (Very Much Improved or Much Improved).

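### Symptom intensity is averaged only over days with an event, so the one graded analysis of prodromal severity is conditional on a post-randomisation outcome and can hide or reverse a benefit

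*SAP*

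**What the plan says.** SAP 7.2.2.3.2 derives the average daily mean intensity of prodromal symptoms. Its first step is "A day without any prodromal symptoms is not qualified". The value at a time point "is the average of the daily mean intensity of qualified days in the corresponding 14 day window". A minimum is also set: "At least 1 day diary data is required for each 14 day window to be qualified for this calculation". The section then extends a similar rule to "The average daily mean intensity of the subject's phototoxic reactions (associated with sun exposure) on an 11-point Likert scale".

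For baseline, the footnote to Table 2 in SAP 7.3 says "If subjects have no data of sunlight exposure between Day -1 and Day -14, then the Analysis Visit window will be expanded to Day -28". The trigger is absence of exposure data, not absence of symptoms.

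SAP 8.2.3 analyses both intensity endpoints, as exploratory endpoints, with an MMRM modelled on the primary analysis. That model (SAP 8.2.1) uses the available data without imputation. The missing-data sensitivity analyses in 8.2.1 are written for the primary endpoint only.

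The primary objective in Protocol 6.1.1 covers "time to onset and severity of first prodromal symptoms". The diary scale in Protocol 10.7.1.1 runs from 0 to 10, "with 0 indicating no pain or discomfort and 10 indicating greatest severity of pain".

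**The concern.** Whether a subject has symptoms on a given day after randomisation is an outcome that the drug is meant to change. Averaging only over days with symptoms selects days, and then whole windows, on that outcome. The arms are then compared on sets of days that randomisation did not make comparable. An empty window enters the MMRM as a missing value, although no intensity existed to be observed.

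The primary endpoint measures time only, so the severity part of the primary objective rests on this derivation for any graded reading of prodromal symptoms. A null or adverse result here could be read as no effect on severity when the drug had removed symptoms altogether. No planned analysis of this endpoint would show that this had happened.

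**Working it through.** The plan gives no effect size, SD or symptom-day rate for intensity, so there is no stated figure to reproduce. The sizing in SAP 3.3 concerns the primary endpoint and does not enter.

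**Step 1: what each rule measures.** Take a window with d exposed days, k of them with symptoms, and let S be the sum of the daily mean intensities.

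- SAP rule: S/k, undefined when k = 0.
- Event-free exposed days scored 0: S/d = (k/d) × (S/k).

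The SAP value has no term for frequency. If the drug removes a symptomatic day rated below S/k, S/k rises while S/d falls, or stays level if that day was rated 0.

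**Step 2: neighbouring rules.** SAP 7.2.2.3.1 qualifies a day by non-zero sunlight exposure and gives a symptom-free exposed day its full exposure time. SAP 7.2.2.3.3 also qualifies by exposure. In 7.2.2.3.4 a symptom-free day adds nothing to the count but stays in the period. Only the intensity rule discards the day.

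**Step 3: baseline.** A subject with exposure but no symptom in Day -14 to -1 has k = 0 and does not trigger the Day -28 extension. Baseline is undefined, so there is no change score at any visit.

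**Step 4: chance of an empty window.** With daily event probability p and independent days, it is (1 - p)^d. Both p and d are assumptions.

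| p | d = 7 | d = 10 | d = 14 |
|---|---|---|---|
| 0.05 | 69.8% | 59.9% | 48.8% |
| 0.10 | 47.8% | 34.9% | 22.9% |
| 0.20 | 21.0% | 10.7% | 4.4% |
| 0.30 | 8.2% | 2.8% | 0.7% |
| 0.50 | 0.8% | 0.1% | 0.0% |

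Empty windows concentrate in subjects with few events. Phototoxic intensity is probably more exposed: Protocol 10.7.2.1 describes these reactions as following a prodrome, and Protocol 8.7.2 says that the aim is not to induce them.

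**Step 5: effect on the treatment difference.** This is a simulation with 200,000 subjects per arm and one window of 10 exposed days. Placebo daily symptom probability p0 is 0.3, 0.5 or 0.8. Subject mean severity is 4 (between-subject SD 1, within-subject SD 1.5), with ratings rounded and limited to 1 to 10. All of these inputs are assumed. Entries are active minus placebo in arm means of window values, at p0 = 0.3 / 0.5 / 0.8; no MMRM was fitted.

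| What the drug does | SAP rule | Event-free days scored 0 | Active windows with no value |
|---|---|---|---|
| Halves symptom days, severity unchanged | 0.00 / +0.01 / 0.00 | -0.61 / -1.01 / -1.61 | 19.7 / 5.6 / 0.6% |
| Same, plus 20% of subjects symptom-free | -0.01 / 0.00 / 0.00 | -0.73 / -1.21 / -1.94 | 35.5 / 24.5 / 20.7% |
| Removes only milder symptoms (below 4) | +1.30 / +1.26 / +1.24 | -0.40 / -0.66 / -1.06 | 25.6 / 12.5 / 5.7% |
| Shifts all severity down by 1.5 | -1.14 / -1.16 / -1.16 | -0.44 / -0.74 / -1.18 | 5.8 / 0.7 / 0.1% |
| Lowers severity by 1, frequency unchanged | -0.92 / -0.91 / -0.92 | -0.28 / -0.46 / -0.73 | 2.8 / 0.1 / 0.0% |
| Removes only more severe symptoms (above 4) | -1.32 / -1.28 / -1.26 | -0.82 / -1.35 / -2.17 | 25.6 / 12.4 / 5.7% |

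Placebo windows with no value: 2.8 / 0.1 / 0.0%.

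The identity in Step 1 checks the table. The placebo mean on symptomatic days is 4.04 at p0 = 0.3. Halving symptom days changes the zero-scored mean by (0.15 - 0.30) × 4.04 = -0.61. Lowering severity by 1 changes it by 0.3 × (-0.92) = -0.28.

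**The case against.** A conditional mean answers a legitimate question: how bad are symptoms when they occur? Severity of a first symptom can naturally be read that way. Removal of symptoms is credited elsewhere, by the primary endpoint, by the event count in H5/H6 and by pain-free hours and days. The plan also treats a symptom rated 0 as different from no symptom, since some endpoints specify ratings of 1 to 10 or severity above 0; scoring event-free days 0 merges the two. Zero-scoring dilutes a pure fall in severity (-0.28 to -0.73 against about -0.92), and a brief, cautious outing would earn the best score. Protocol 8.7.2 asks subjects to stay out until some symptoms appear, which makes empty prodromal windows rarer. All of this stands. It argues against replacing the endpoint, not against adding a second version.

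Three stronger readings are tempting, and the documents do not support them.

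- **These are the only severity analyses.** The SAP also plans total and maximum severity of phototoxic reactions, PROMIS-57 pain intensity (H7/H8), the count of prodromal events rated 1 to 10 (H5/H6) and PGIS. None of these is a graded measure of prodromal intensity.
- **The rule is biased against an effective drug.** The direction depends on which symptoms the drug removes, and nothing in the documents settles that.
- **The best responders drop out.** They lose windows. Their symptomatic windows stay in the MMRM, which also uses their baseline. Subjects are lost entirely only if they have no baseline value or no symptomatic window after baseline.

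**Conclusion.** The point holds as a limitation of the endpoint definition. As written, the analysis estimates severity given that symptoms occurred, in a set of days and windows that treatment can change. It can hide a benefit that comes from fewer symptom days (about 0.00 where the zero-scored difference is -0.61 to -1.61) and reverse the sign if milder symptoms go first (about +1.3). It still shows a fall in severity on symptomatic days (about -0.9 for a one-point fall). These sizes rest entirely on the assumed inputs; they show what can happen, not what to expect in this trial. The structural part needs no assumption: empty windows and symptom-free baselines have no value, and no sensitivity analysis is planned for that. Both endpoints are exploratory and outside H1 to H12, so no confirmatory conclusion changes. The addition is still worth making, because the primary objective names this severity.

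**What to change.** For both intensity endpoints:

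1. Add an MMRM on a version that qualifies a day by non-zero sunlight exposure, as in SAP 7.2.2.3.1, and scores an exposed day without the event as 0. Derive its baseline in the same way.
2. Report the number of windows, and of baselines, without a value under the current rule, by arm and visit.
3. Label the current endpoint as conditional on symptoms (or on a phototoxic reaction) in the SAP and in the outputs.

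Show the two versions side by side. The zero-scored version mixes frequency with intensity and counts brief, cautious exposure as 0, so it should not replace the conditional mean. If the Week 26 results are already unblinded, mark the addition as post hoc.

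The cost is one derivation rule, a repeat of an existing model for two endpoints, and one table. No new data are needed.

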6.1.3 Exploratory Objectives

- To investigate the effect on sunlight exposure duration in adults and adolescents with EPP or XLP.
- To investigate the effect on melanin density in adults and adolescents with EPP or XLP.
- To investigate the PK/pharmacodynamic (PD) relationship in adults and adolescents with EPP or XLP.
- To investigate the effect of mutations in MC1R gene on sunlight exposure duration and melanin density in adults and adolescents with EPP or XLP.

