Fitzpatrick skin type assessment ^s	X		X		X		X	X		X	X
Pregnancy test ^t	X	X	X		X		X	X		X	X
PK sampling (blood) ^y		X		X		X	X		X	X	
Blood sampling for PGx ^b		X									
Dispensing of study medication	X	X	X		X		X	X		X	
Medication accountability		X		X		X		X		X	
Subject Question for study medication ^k						X					
PROMIS-57		X				X	X		X	X	X
PGIC				X			X			X	
PGIS		X	X		X		X		X	X	X
EOT/Exit interview questionnaire ^l						X					
Sunlight exposure diaries ^m											
In-clinic sunlight exposure test ⁿ	X									X	

Study Period	Screening		Double-blind Treatment					Double-blind Extension			Follow-up	
	Visit Number	Visit 1	Visit 2 (Randomization)	Visit 3 ^g	Visit 4	Visit 5 ^g	Visit 6	Visit 7 ^h (EOT/ Rand)	Visit 8 ^g	Visit 9 ^g	Visit 10	
Study Week	Week -6 to Week 0		Week 2	Week 4	Week 8	Week 12	Week 26	Week 28	Week 32	Week 39	Week 52	Week 32 or 58
Study Day ± Window	Day -42 to Study Day ^a	Day 1	Day 15±5	Day 29±7	Day 57±7	Day 85±7	Day 183±7	Day 197±7	Day 225±7	Day 274±7	Day 365±7	Day 407±7
Melanin density evaluation		X		X		X	X				X	X
Nevi evaluation ^o		X		X		X	X				X	X
Concomitant medication												
Adverse events												

Abbreviations: DBE = double-blinded extension; ECG = electrocardiogram; EOS = end of study; EOT = end of treatment; PGIS = Patient Global Impression of Change; PGIS = Patient Global Impression of Severity; PGx = pharmacogenomic(s); PK = pharmacokinetic; PROMIS = Patient-Reported Outcomes Measurement Information System.

^a A minimum of 7 days of outside exposure data is required in the 14 days prior to randomization.

^b Blood samples will be collected for PGx analysis for those subjects who have specifically given informed consent/assent for optional PGx analysis at Visit 2.

^c Complete physical examination will be performed at Visit 1 and an abbreviated physical examination will be performed at all other specified time points.

^d Vital signs include measurement of sitting blood pressure, respiratory rate, pulse rate, and body temperature.

^e ECG will be assessed at Visit 7 for subjects who do not elect DBE. For subjects that received MT-7117 during the blinded period will continue the DBE in the same treatment arm and remain blinded. Subjects that received placebo will be randomized to receive MT-7117 [REDACTED] or [REDACTED] in 1:1 ratio for the 26 weeks DBE period. For subjects with the [REDACTED] dose will be administered without re-randomization.

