14.3 Statistical Analysis Methods

A SAP containing details of all the analyses and outputs will be prepared and approved before the study database lock. The ITT population will be used for all efficacy analyses. All safety analysis will be performed on the Safety population.

Unless otherwise specified, the baseline values will be the last non-missing value before receiving the first dose of study medication.

Baseline for an efficacy endpoint based on sunlight exposure time will be the mean of the daily value of the endpoint in a 14-day window before Day 1. Similarly, for this endpoint, their values at each post-baseline time point (Week 2, 4, 6, 8, 10, 12, 14, 16, 18, 20, 22, 24, 26, 52, and 58) are the mean of the daily value of the endpoint in a 14-day window on or before the visit.

To calculate the average daily duration, a 14-day window on or before time point (Week 2, 4, 6, 8, 10, 12, 14, 16, 18, 20, 22, 24, and 26) will be used.

Continuous endpoints will be summarized with the descriptive statistics (the number of observations, mean, standard deviation (SD), median, minimum, and maximum). Categorical endpoints will be summarized using frequency counts and percentages.

All statistical tests will be 2-sided with 5% significance level. Point estimates of treatment differences will be provided with 2-sided 95% confidence intervals (CIs) where applicable.

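### The exploratory average daily duration of symptom-free sun exposure leaves out days without exposure, so it measures minutes per exposed day and can stay flat or fall when subjects go out more often

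*SAP*

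**What the plan says.** SAP 7.2.2.3.3 derives this endpoint in four steps. Step 1 lifts the daytime restriction that applies to the primary endpoint. Step 2 selects the days: "A diary day is qualified if the subject had non-zero duration of sunlight exposure in the day". Step 3 sets the daily value: "It is the sum of the duration of sunlight exposure time deducting the prodromal symptom or phototoxic reaction presenting time covered in each period". Step 4 borrows the averaging from the primary endpoint: "Step 4 to 5 in section 7.2.2.3.1 will be applied". In SAP 7.2.2.3.1 step 4, that average is taken over the values "of qualified days in the corresponding 14 day window", and very little data is needed: "At least 1 day diary data is required for each 14 day window to be qualified for this calculation".

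Protocol 14.3 is less specific. For endpoints based on sunlight exposure time, it says the post-baseline values "are the mean of the daily value of the endpoint in a 14-day window on or before the visit". It gives no rule for a day without exposure.

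The endpoint is a change from baseline at Week 26. It is listed as exploratory in Protocol 6.2.3 and SAP 2.3.3 and analysed by ANCOVA or ANOVA (SAP 8.2.3). An extension version (SAP 2.3.4) is summarised descriptively. It bears directly on the first exploratory objective in Protocol 6.1.3: "To investigate the effect on sunlight exposure duration in adults and adolescents with EPP or XLP".

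Two provisions concern how often subjects go out. Protocol Table 9-1, footnote a, states: "A minimum of 7 days of outside exposure data is required in the 14 days prior to randomization". Protocol 8.7.2 asks subjects to go outside at least once a day during treatment.

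**The concern.** The day filter suits the primary endpoint. Time to a first symptom does not exist on a day without exposure, so there is nothing to average. A duration of exposure does exist on such a day: it is zero. Once those days are filtered out, the quantity is no longer minutes per day but minutes per day on which the subject went out.

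Whether to go out is decided after randomisation, and treatment may influence it. A drug that makes patients confident enough to go out more often would be expected to add outings, some of them short. Extra outings of typical length leave the endpoint unchanged, and extra short ones pull it down, although symptom-free time in the sun has risen in both cases. A reader who takes the label at face value could conclude that the drug had no effect on daily exposure, or a harmful one.

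This is also the only diary endpoint that expresses total symptom-free exposure duration as a change from baseline.

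**Working it through.** The plan states no figure for this endpoint, so there is none to reproduce. The check applies the rule directly.

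**Inputs**
- Window of 14 days (SAP Table 2).
- k = number of days in the window with non-zero exposure; these are the only qualified days (SAP 7.2.2.3.3 step 2).
- S = sum of symptom-free minutes over the window (step 3).
- The minutes and day counts below are assumptions, and all 14 diary days are assumed complete. A baseline of 7 exposed days is the lowest the entry rule allows, if that rule means days with actual exposure.

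**Formulas**
- SAP value = S / k
- Per diary day = S / 14 = (k / 14) × SAP value

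**Results** (minutes; days × minutes per day)

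| Baseline | Follow-up | S | SAP rule | Change | Per diary day | Change |
|---|---|---|---|---|---|---|
| 7×60 | 10×60 | 420 → 600 | 60 → 60 | 0 | 30 → 42.9 | +12.9 |
| 7×60 | 7×60 + 3×30 | 420 → 510 | 60 → 51 | −9 | 30 → 36.4 | +6.4 |
| 7×60 | 14×60 | 420 → 840 | 60 → 60 | 0 | 30 → 60 | +30 |
| 7×60 | 7×60 + 7×20 | 420 → 560 | 60 → 40 | −20 | 30 → 40 | +10 |
| 12×60 | 12×60 + 2×20 | 720 → 760 | 60 → 54.3 | −5.7 | 51.4 → 54.3 | +2.9 |
| 7×60 | 14×80 | 420 → 1120 | 60 → 80 | +20 | 30 → 80 | +50 |

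Second row in full: (7×60 + 3×30) / 10 = 510 / 10 = 51, and 510 / 14 = 36.4.

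**When the sign reverses.** Suppose exposed days go from k0 to 14 and mean minutes per exposed day are multiplied by r. The SAP value falls when r < 1. Total symptom-free time rises when (14 / k0) × r > 1, that is, when r > k0 / 14. The two disagree for r between k0/14 and 1:
- k0 = 7: 0.50 to 1
- k0 = 10: 0.71 to 1
- k0 = 12: 0.86 to 1

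The range narrows as baseline outdoor days approach 14. The last row of the table shows that if minutes per exposed day also rise, the SAP rule still shows a gain, though a smaller one.

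**Window with no outings.** A subject who completes the Week 26 diary but never goes out has no qualified day and therefore no value. Per diary day the value is 0.

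**The case against.** The strongest reply is that frequency of going out is measured elsewhere. The SAP has total symptom-free hours over 26 weeks, a sum to which an indoor day adds nothing (7.2.2.3.5), and total days outdoors (2.3.3). Every example above in which outdoor days increase would show as a gain in days outdoors and, for daytime exposure, in total hours. This largely stands, but neither is an exact substitute. Total hours covers only the daytime window and is exempt from baseline adjustment (SAP 8.2.3), and days outdoors carries no minutes.

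A second reply is that the examples are unfavourable. Subjects are asked to go out daily, and those unwilling or unable to do so on most days are excluded (Protocol 8.4). If the 7-day entry rule means days with exposure, outdoor days can at most about double from baseline. This also stands, so the figures are illustrations and not expectations. No similar floor applies after baseline, where one qualified day gives a window value.

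Third, counting zeros requires the diary to record that no exposure took place. Protocol 10.7.1.1 says the diary is completed daily, but it describes entries made for each exposure, and the sample questions in Appendix 4 are redacted. If indoor days leave no record, scoring them as zero would turn missed entries into lost sun time. This stands and makes the fix conditional.

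Three stronger readings are tempting, and the documents do not support them:
- **The SAP contradicts the protocol.** Protocol 14.3 does not define the daily value on a day without exposure. The SAP fills that gap, and SAP 1 says its analysis details take precedence.
- **The exposure-duration objective rests on this measure alone.** The primary and in-clinic endpoints are also changes from baseline in exposure minutes, although up to the first symptom, and the totals above add further information.
- **The primary endpoint has the same fault.** The sentence is the same, but leaving out days without exposure is defensible there.

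**Conclusion.** The point holds for this one exploratory endpoint. As derived, it is symptom-free minutes per day with exposure. It conditions on a post-randomisation choice and can show no change or a fall while total symptom-free time rises. That it can do so follows from the rule alone. How far it would do so in this trial cannot be judged, because the documents give no distribution of outdoor days. The effect is small if most subjects already go out on nearly all days and larger if baseline is near 7 of 14.

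The endpoint is outside the H1 to H12 sequence, so no primary or secondary conclusion changes. What is at risk is the reading of the only diary measure of total symptom-free exposure duration expressed as a change from baseline.

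**What to change.** Change step 2 of SAP 7.2.2.3.3 so that every completed diary day qualifies. A completed day without exposure contributes 0 minutes, and a day with no entry is missing. Apply this at baseline and at all visits, including the extension version. Keep the mean over exposed days only as a supplementary table, and leave the primary endpoint's rule unchanged.

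The sponsor must first confirm that the diary data separate a day without exposure from a missed entry. If they do not, keep the present calculation, relabel the endpoint as per day with exposure, and report the number of exposed days per window by arm beside it.

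The cost is one SAP sentence and a small programming change on diary data already collected, provided that separation is possible. The fallback costs a label and one extra summary row.
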